The risks are the side effects associated with each drug. For prochlorperazine, this includes drowsiness, blurred vision, xerostomia, congestion, nausea, akathisia, tardive dyskinesia, NMS, and blood dyscrasias. For Benadryl include sedation, tiredness, sleepiness, dizziness, constipation, dry mouth, blurred vision, nausea, and loss of appetite. For normal saline, this

includes injection site swelling, redness, infection, venous thrombosis or phlebitis or hypervolemia. Personal benefits include intended reduction in headache symptoms and the satisfaction that the patient may be assisting investigators in determining a more effective headache treatment.

Interventions

After enrollment, each patient will be randomized either to the standard treatment arm to receive prochlorperazine 0.15 mg/kg up to 10 mg IV along with diphenhydramine 1mg/kg (up to 50 mg) IV and normal saline at 5 mL/h IV OR to the study arm to receive prochlorperazine along with diphenhydramine IV and normal saline at 20 mL/kg (up to 1000 mL) given IV over 1 hour. The diphenhydramine will be administered first, and immediately afterward the prochlorperazine will be administered. The patient will then be connected to normal saline on an IV pump and randomized to 5 cc over an hour or 20 cc/kg (maximum 1000 cc) over one hour. The IV bag and pump will be covered so that the patient will not know how much fluid they are receiving. Patients will undergo simple randomization to either the fluid bolus group or the control group. The treating physician will consult a folder that contains a list specifying the group assignment. Each row of the list corresponded to a patient, and will be covered by a small slip of opaque paper that will be removed at the time of enrolment to reveal the group assignment. This list was constructed at the beginning of the study using a random number generator by a research staff. Randomization in the pediatric ED and adult ED will be separate to ensure equal numbers of pediatric patients in both the experimental and control arms (blocking). Emergency providers will be instructed not to administer any rescue medications for at least 30 minutes.

Safety

After 30 minutes, the treating provider will be permitted to administer a “rescue medication” of their choice for further treatment. If there is an untoward event that requires the patient to know which IVF dose was administered, patient will unblinded and will not continue in the study.

Reportable Events

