Anticipated side effects are those listed on the manufacturer’s package insert and are treated as routine non-urgent or non-emergent events are not reportable events.

Adverse Events are those unanticipated side effects that require interventions or anticipated side effects that do not respond to intervention.

Serious Adverse Events are those side effects that require Advanced Life Support measures to control symptoms.

AEs and SAEs will be reported to the IRB within 5 days of the event.

Methods of Measurement

Enrolled patients will fill out a brief data collection form to include age, sex, race, phone number, and baseline headache severity using a 100-mm visual analog scale (VAS). Repeat headache severity scores will be measured at 30 and 60 minutes. Time zero begins immediately after complete administration of the study drug. Nausea (with a 100 mm VAS) and vomiting will also be assessed at these time intervals. The need for rescue medications will be extracted from the patient's chart at a later time.

Trained research assistants will call the patient 24-48 hours post-discharge by phone to ask if they are currently having a headache (yes or no) and to rate their current pain (0-10). If the patient is admitted, the patient will be approached in the hospital by an investigator or research assistant for follow up.

Outcome Measures

The primary outcome measure will be the difference in pain scores between the 5 cc over an hour and 20 mg/kg (up to 1000 cc) over an hour groups measured as the absolute difference between the means at 60 min. Secondarily, we will measure the difference between the rates of decline in pain scores, rate of admission, nausea scores, rate of vomiting, rate of use of additional medications for headache, and headache resolution with telephone follow up.

Privacy and Security

In order to protect the privacy of the research subjects and to maintain the confidentiality of data, all data will be managed only by trained research assistants or investigators and will be stored in the locked Emergency Medicine research offices and electronic data will be stored on a password protected computer in the locked Emergency Medicine research office. All research assistants and investigators are HIPAA- trained, CITI trained and credentialed by UMC IRB, and oriented to the study protocol.

Data Analysis:

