Assuming a SD of 22 (based on prior data from our institution), we calculated that we would need 45 patients in each group to find a clinically important difference in pain score reduction (13 mm) between groups at 60 min with at least 80% power and an alpha of 0.05.

The groups will be compared using a t -test on gender, race, and age; and a chi (with Yates correction)-squared test on severity of presenting headache, to determine if they are similar. The individual VAS measurements will be compared using a repeated measures analysis of variance (ANOVA) test.

REFERENCES

[1] R.B. Lipton, M.E. Bigal, M. Diamond, F. Freitag, M.L. Reed, W.F. Stewart, et al. Migraine prevalence, disease burden, and the need for preventive therapy. *Neurology*, 68 (2007), pp. 343–349

[2] B.W. Friedman, J. West, D.R. Vinson, M.T. Minen, A. Restivo, E.J. Gallagher. Current management of migraine in US emergency departments: an analysis of the National Hospital Ambulatory Medical Care Survey. *Cephalalgia*, 35 (2015), pp. 301–309

[8] Jones J, et al. Randomized double-blind trial of intravenous prochlorperazine for the treatment of acute headache. *JAMA*. 1989;261:1174-1176.

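### The only analysis named for the outcome pain scores is a repeated-measures ANOVA with no term or 60-minute contrast, so the primary outcome has no pre-stated test

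*Combined protocol and SAP*

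**What the plan says.** The Outcome Measures section defines the primary outcome as the difference in pain scores between the two fluid groups, "measured as the absolute difference between the means at 60 min". It then lists a trajectory outcome as secondary: "Secondarily, we will measure the difference between the rates of decline in pain scores".

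The Data Analysis section sizes the trial at 45 per group for a "clinically important difference in pain score reduction (13 mm) between groups at 60 min", with SD 22, at least 80% power and alpha 0.05.

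The same section names three procedures. Two are baseline checks: a t-test on gender, race and age, and a Yates-corrected chi-"squared test on severity of presenting headache, to determine if they are similar". The third is the only one for outcome scores: "The individual VAS measurements will be compared using a repeated measures analysis of variance (ANOVA) test". Pain is scored at baseline, and under Methods of Measurement "Repeat headache severity scores will be measured at 30 and 60 minutes".

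Two provisions under Safety affect which 60-minute scores exist and what they reflect. A patient who has to be told the fluid dose after an untoward event is taken out: "patient will unblinded and will not continue in the study". And rescue can precede the primary score: "After 30 minutes, the treating provider will be permitted to administer a" rescue drug of their choice.

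**The concern.** A repeated-measures ANOVA on two groups yields several p-values. The group effect compares the arms averaged over the time levels. The group-by-time term tests for any difference in the shape of the profiles. Neither is the difference at 60 minutes. The plan does not say which term decides, whether baseline is one of the time levels, or whether a 60-minute contrast follows.

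Three things are at stake:

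- The stated power belongs to a two-sample comparison at 60 minutes and does not carry over to either ANOVA term.
- A significant omnibus result can come from 30 minutes, from 60 minutes or from both, and the term can be picked after the results are known.
- With no interval planned for the 60-minute difference, a null result need not show whether 13 mm has been excluded, which is the clinical question.

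The analysis sentence also does not say which patients are compared, although the Safety section lets some leave and lets others receive rescue before the primary score.

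**Working it through.** **Inputs from the protocol (Data Analysis).** 45 per arm, difference 13 mm, SD 22, 80% power, alpha 0.05 (taken as two-sided; one-sided would need only 36).

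**Assumptions, because the documents do not give these.** SD 22 at each time; equal within-patient correlation ρ of 0.3, 0.5 or 0.7; the effect profiles shown below; all 90 patients scored.

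**1. The plan's own figure.** n per arm = 2 × [22 × (1.960 + 0.842) / 13]² = 44.96, so 45. By noncentral t with 88 df, the standard error is 22 × √(2/45) = 4.64, the noncentrality is 13 / 4.64 = 2.80, and power is 79%. The stated size is therefore that of a two-sample comparison of means at one time.

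**2. Formulas for the ANOVA terms.**
- Group effect: noncentral t, 88 df. The effect is the mean of the profile. The SD is 22 × √((1 + 2ρ)/3) with three time levels, or 22 × √((1 + ρ)/2) with two.
- Group-by-time: noncentral F with noncentrality (45/2) × Σd² / (22² × (1 − ρ)), where d is the profile centred on its mean. The df are (2, 176) with three levels and (1, 88) with two.

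**3. One case in full: 0/6.5/13 mm at 0/30/60 minutes, ρ = 0.5.**
- Group-by-time: d = −6.5, 0, 6.5, so Σd² = 84.5. Noncentrality = 22.5 × 84.5 / (484 × 0.5) = 7.86; power 70%.
- Group effect: mean 6.5, SD 22 × √(2/3) = 17.96, noncentrality 6.5 / (17.96 × √(2/45)) = 1.72; power 40%.
- 60-minute test: 79%.

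Reversing the last two values (0/13/6.5) leaves the mean and Σd² unchanged, so both ANOVA powers are identical. The 60-minute noncentrality falls to 6.5 / 4.64 = 1.40 and its power to 28%.

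**4. Results, percent significant at ρ = 0.3 / 0.5 / 0.7.**

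| Profile at 0/30/60 min (mm) | Time levels | Group-by-time | Group effect | Unadjusted 60-min test |
|---|---|---|---|---|
| 0/6.5/13 | 0, 30, 60 | 55 / 70 / 91 | 48 / 40 / 34 | 79 |
| 0/13/6.5 | 0, 30, 60 | 55 / 70 / 91 | 48 / 40 / 34 | 28 |
| 0/6.5/13 | 30, 60 | 22 / 28 / 43 | 73 / 67 / 62 | 79 |
| 0/13/6.5 | 30, 60 | 22 / 28 / 43 | 73 / 67 / 62 | 28 |
| 0/13/0 (extreme) | 0, 30, 60 | 68 / 83 / 97 | 24 / 20 / 18 | 5 |
| 0/6.5/0 | 0, 30, 60 | 21 / 28 / 44 | 10 / 9 / 8 | 5 |
| 0/13/13 (sustained) | 0, 30, 60 | 68 / 83 / 97 | 72 / 62 / 54 | 79 |
| 0/13/13 (sustained) | 30, 60 | 5 / 5 / 5 | 93 / 89 / 85 | 79 |

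The match between mirrored profiles does not depend on all correlations being equal. It needs equal SDs at 30 and 60 minutes and equal correlation of each with baseline. With baseline-to-post correlation 0.5 and 30-to-60 correlation 0.75, a 20,000-replicate simulation gave group-by-time 75.5% and 75.3%, and group effect 37.3% and 36.8%, for the two mirrored profiles. The 60-minute test gave 79% and 28%.

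**5. What a 60-minute analysis delivers.** Unadjusted, the 95% half-width is 1.987 × 4.64 = 9.2 mm, so an observed benefit below 13 − 9.2 = 3.8 mm would exclude 13 mm. Adjusted for baseline at ρ = 0.5, the residual SD is 22 × √(1 − 0.25) = 19.05, the half-width 8.0 mm and the power 89% (86 df, allowing for baseline and emergency department). If about 10% lack a 60-minute score (41 per arm, assumed), power is 75% unadjusted and 86% adjusted, with half-widths 9.7 and 8.4 mm.

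**6. Meaning of SD 22.** The outcome is a mean at 60 minutes, but the sizing sentence speaks of a reduction. If 22 is the SD of the raw score, the SD of the change is 22 × √(2(1 − ρ)) = 26.0 / 22.0 / 17.0, and a t-test on change has power 65 / 79 / 95%.

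**The case against.** The protocol already fixes the outcome, the time, the summary measure, the 13 mm target and alpha. A comparison of individual measurements may mean one comparison per time, which would include 60 minutes, and a 60-minute contrast after a repeated-measures ANOVA is ordinary practice. On that reading the plan lacks a clarification and does not name a wrong test. Nothing shows that a post hoc choice of term was intended. This stands as a possible reading, but the sentence does not state it. Even if it did, it would give comparisons at more than one time without marking the 60-minute one as decisive.

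The fading profiles may also be thought unlikely: the bolus runs over an hour, so an effect peaking at 30 minutes is hard to expect if the clock starts once prochlorperazine is in. The start of the clock, after the study drug, is itself ambiguous. The point about balance is fair, and sustained profiles are in the table for that reason. Some ANOVA choices then exceed 79%, while another has 5%, so dependence on the unstated choice remains.

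Three smaller points stand. The gain from baseline adjustment is no measure of this defect. No figure supports a gain from adjusting for emergency department. And a reader could derive an interval from reported 60-minute means, SDs and numbers, so its absence from the plan does not make it unobtainable. Rescue use, the analysis set and the meaning of SD 22 are related questions that naming a test does not settle.

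**Conclusion.** The concern holds. The primary outcome and the sample size refer to 60 minutes, and no sentence in the plan names a test or interval for that difference. The sample size itself is not in dispute, since 45 per arm reproduces.

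Across the profiles tabulated, all with 13 mm or less at either time, the ANOVA terms run from 5% to 97% significant depending on the term, the time levels and the correlation. They cannot distinguish an effect mainly at 60 minutes from its mirror image mainly at 30 minutes. These percentages rest on the assumed SDs, correlations and profiles and are illustrations. That the group effect and the group-by-time term do not test the 60-minute difference does not depend on them. Because this is the trial's single primary inference, it must be settled before outcome data are examined by arm.

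**What to change.** Name one primary analysis in Data Analysis. Suggested wording:

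> The primary analysis is a linear model of 60-minute VAS on arm, baseline VAS and emergency department (adult or pediatric). Patients are analysed in their assigned arm, and every randomised patient with a 60-minute score is included. The number without one is reported by arm. The adjusted mean difference is given with its 95% confidence interval and read against 13 mm.

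The minimum that matches the outcome and sample size is an unadjusted 60-minute difference with a 95% interval. Baseline adjustment gains precision and is not a condition of validity. The emergency department term reflects the separate randomisation in the two departments.

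In addition:
- State how 60-minute scores recorded after rescue enter the analysis. Using them as recorded, with rescue use shown by arm beside the result, is the simplest match to the stated outcome.
- Keep the repeated-measures ANOVA for the secondary rate-of-decline outcome, and name its time levels and the term tested.
- State whether SD 22 refers to the score or to the reduction.

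The cost is a few sentences. Baseline VAS is on the data form, the department is known from randomisation, and rescue use is already taken from the chart. No new data and no more patients are needed.

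### The repeated measures ANOVA named for the VAS, as ordinarily run, discards patients with any missed reading and can push the secondary group-by-time test above 5%; a baseline-adjusted mixed model with a 60-min contrast avoids both

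*Combined protocol and SAP*

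**What the plan says.** All places are in the combined protocol and SAP.

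- **Readings.** Methods of Measurement has each patient record "baseline headache severity using a 100-mm visual analog scale (VAS") and then states "Repeat headache severity scores will be measured at 30 and 60 minutes". That makes three occasions.
- **Outcomes.** Outcome Measures defines the primary outcome as the pain difference between the two fluid groups, "measured as the absolute difference between the means at 60 min". It then adds "Secondarily, we will measure the difference between the rates of decline in pain scores", among other secondary outcomes.
- **Analysis.** Data Analysis says "The individual VAS measurements will be compared using a repeated measures analysis of variance (ANOVA) test". No other test is named for the VAS. The documents do not say which occasions enter, which term or contrast tests the 60-min difference, what happens to a patient with a missed reading, who forms the analysis population, or whether a sphericity correction is applied.
- **Sample size.** Data Analysis sets 45 per group, "Assuming a SD of 22 (based on prior data from our institution"), to detect a "clinically important difference in pain score reduction (13 mm) between groups at 60 min". No allowance for loss is stated.
- **Routes to missed readings.** Risk/Benefit lists drowsiness for prochlorperazine and, for diphenhydramine, "For Benadryl include sedation, tiredness, sleepiness, dizziness". Under Safety, a patient unblinded after an untoward event leaves the study. No expected rate is given for either route.

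**The concern.** Two properties of repeated measures ANOVA, in its usual form, fit this design poorly.

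First, it needs a full set of readings per patient. A patient with a 60-min score but no 30-min score drops out of the analysis even though the primary outcome was measured. A patient with a 30-min score but no 60-min score contributes nothing. The sample size has no slack, so each deletion costs power. If the deletions are related to pain and differ between arms, they also distort the 60-min comparison.

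Second, with three occasions the within-patient F tests assume that all pairwise differences between occasions have the same variance. One score before treatment and two scores taken 30 min apart after it are unlikely to meet this. Without a correction, the group-by-time p-value is then too small. That test is the natural one for the secondary rate-of-decline outcome.

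**Working it through.** **1. The plan's sample size.** Inputs from Data Analysis: difference 13 mm, SD 22 mm, alpha 0.05 (taken as two-sided), power 80%.

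n = 2 × (1.960 + 0.842)² × 22² / 13² = 2 × 7.849 × 484 / 169 = 44.96, so 45 per group. The stated figure reproduces. The exact t-test power is 79.2% at 45 per group and 80.1% at 46, so there is nothing in reserve.

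**2. Power lost by requiring every reading.** The documents give no loss rate. Assume 5% missing at 30 min and, independently, 5% missing at 60 min, with baseline always present.

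- All readings present: 0.95 × 0.95 = 0.9025, and 0.9025 × 90 = 81.2, so about 81 patients.
- 60-min score present: 0.95 × 90 = 85.5, so about 86 patients.

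| Patients per arm | t-test power, 13 mm, SD 22 |
|---|---|
| 45 (no loss) | 79.2% |
| 43 (all with a 60-min score) | 77.3% |
| 41 | 75.3% |
| 40 | 74.2% |

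Deleting patients who have a 60-min score therefore costs about 2 points. Over a wider range, if the share of patients dropped for any reason is 5%, 10% or 20%, power is 77.0%, 74.8% or 69.6%. These are two-sample t-test powers, used as a guide; they are not powers of the ANOVA or of a mixed model.

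**3. Type I error of the group-by-time test.** Departure from sphericity is measured by epsilon, which for three occasions lies between 0.5 and 1 (1 means sphericity holds). As an example, assume SDs of 20, 22 and 22 mm and correlations of 0.5 (baseline with 30 min), 0.4 (baseline with 60 min) and 0.8 (30 with 60 min). The variances of the differences are:

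- baseline and 30 min: 400 + 484 − 2 × 0.5 × 20 × 22 = 444
- baseline and 60 min: 400 + 484 − 2 × 0.4 × 20 × 22 = 532
- 30 and 60 min: 484 + 484 − 2 × 0.8 × 22 × 22 = 193.6

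They are far from equal, and epsilon is 0.787. Rejection rates in simulated trials with no true effect, 45 per arm, 100,000 trials per row:

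| Assumed pattern | Epsilon | Uncorrected | Greenhouse-Geisser |
|---|---|---|---|
| Equal SDs, all correlations 0.5 | 1.00 | 5.0% | 4.9% |
| AR(1), correlation 0.5 | 0.93 | 5.4% | 4.9% |
| AR(1), correlation 0.7 | 0.88 | 5.6% | 4.9% |
| AR(1), correlation 0.9 | 0.82 | 5.8% | 4.9% |
| SDs 18/24/26, correlations 0.4/0.3/0.8 | 0.78 | 6.1% | 4.9% |
| SDs 15/25/28, correlations 0.3/0.2/0.85 | 0.70 | 6.5% | 4.9% |
| Extreme: equal SDs, correlations 0.2/0.2/0.95 | 0.55 | 7.9% | 4.9% |
| Near the floor | 0.50 | 8.5% | 5.0% |

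Separate runs of 20,000 trials gave 6.2% for the worked example and 6.7% at epsilon 0.70. The ceiling can be checked directly: at epsilon 0.5 the statistic follows F(1, 88) but is compared with the 5% point of F(2, 176), which gives 8.4%. If only the 30- and 60-min readings enter, sphericity holds automatically (4.9% simulated).

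**4. Bias in the 60-min difference from complete cases.** All loss patterns here are assumed.

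- *Random loss of 10% or 20%:* no bias.
- *Loss linked to low 30-min pain by the same rule in both arms:* none under no effect; 12.8 and 12.7 mm against a true 13 mm at 10% and 20% loss.
- *Loss linked to low 30-min pain in one arm, random in the other:* under no effect, a shift of 1.3 mm at about 10% loss and 2.6 mm at about 20%. In the second case a 60-min t test rejects in 8.0% of null trials.
- *SDs and correlations of the worked example; patients below 30 mm at 30 min miss the 60-min score in 30% (bolus) or 10% (control):* a false difference of about 1.4 mm, and 0.8 to 1.7 mm as the assumed 30-min mean runs from 20 to 55 mm. Regression on baseline and the 30-min score, which uses the information a likelihood-based model would use, leaves under 0.1 mm.

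**The case against.** The strongest reply is that the plan is silent rather than wrong. It does not say the ANOVA will be uncorrected or limited to complete cases, and it does not say that baseline is one of the repeated levels. With a Greenhouse-Geisser correction, or with only two levels, the inflation disappears. This stands, and it is why the point is worded as what the method can do as ordinarily run. Even so, a corrected ANOVA would still delete incomplete patients and would still not name the 60-min contrast.

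A reader might infer that the primary test runs above 5% because of sphericity. The documents do not support that. The primary outcome compares two group means at a single time, and sphericity plays no part in such a comparison.

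A reader might also infer that patients will be dropped selectively, since both background drugs sedate. The documents do not support that either. Under Interventions both arms receive both drugs, so sedation gives no evident reason for loss to differ by arm, and equal loss produced almost no bias. Patients are on a pump for an hour and are enrolled only when trained staff are present, so loss may be low. That argument is weaker if the clock starts after the saline, which the definition of time zero leaves open. Withdrawal after unblinding remains one route by which loss could differ by arm, but no rate is given. Nor is this bias peculiar to ANOVA: any 60-min analysis that ignores the 30-min score shares it.

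Finally, the sizes are modest. A 1.4 mm bias is about a tenth of the 13 mm target (1.4 / 13 = 0.11), and the avoidable power loss is about 2 points.

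**Conclusion.** The concern holds in a conditional form. The only VAS analysis named would, as ordinarily run, delete patients whose primary score was observed, and it carries a sphericity assumption that these three readings probably do not meet. Neither is guaranteed to do harm.

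- **Power:** about 75% instead of about 77%, if 5% of readings are missed at each of 30 and 60 min.
- **Type I error:** about 5.4% to 6.7% under moderate assumed patterns, at most about 8.5%. This needs three levels, non-sphericity and no correction, and it affects only the secondary rate-of-decline comparison.
- **Bias at 60 min:** about 1 to 3 mm, only if loss depends on pain and does so differently in the two arms.

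The loss rates, SD patterns and correlations are assumptions, because the documents give only the SD of 22 mm. The case for changing the method rests on a small expected harm and a very small cost.

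**What to change.** Replace the repeated measures ANOVA with a linear mixed model fitted by REML:

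- outcomes: VAS at 30 and 60 min;
- terms: arm, time, arm-by-time, baseline VAS and baseline-by-time;
- unstructured covariance between the two readings;
- all randomised patients with at least one post-baseline score, analysed in the arm assigned;
- primary test: the arm difference at 60 min from this model.

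This assumes no sphericity, keeps partial data and estimates the primary outcome directly. The cost is a sentence or two of analysis text, slightly more programming, and reliance on data being missing at random given baseline, arm and the observed score. That is a weaker assumption than deletion of incomplete cases generally needs.

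An acceptable simpler alternative is a baseline-adjusted comparison at 60 min using every available 60-min score, with a Greenhouse-Geisser correction stated for the group-by-time test. It keeps patients who miss only the 30-min reading and removes the inflation. It does not use the 30-min score of patients who lack a 60-min score, so it would not protect against loss that depends on 30-min pain and differs by arm.
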